The Sponsor's feasibility study for which the study device, eCoin[™], was implanted in 46 subjects showed a benign safety profile. In particular, no infection at the implant site occurred that required explant. At the time of this writing, all subjects have been followed for at least six months since implantation of the study device. Given that the primary safety concern is infection and that all serious infections are expected to occur by one month after implantation, the adverse event information compiled thus far is promising. Three serious adverse events (SAEs) have occurred: one unrelated pneumonia incident, one unrelated limp due to underlying bursitis of the hip present at screening, and one related cellulitis of the calf secondary to the ankle support suggested as post-operative care. See Attachment 04-32 for additional information on safety. Furthermore, given the expected therapeutic similarity of percutaneous nerve stimulation of the tibial nerve to eCoin[™] stimulation of the tibial nerve, the therapy is not expected to cause adverse events. Nonetheless, safety will be reported through adverse event reporting for the study duration.

While an important benefit to the eCoin[™] system is that delivery of therapy does not require the patient to operate a percutaneous device and locate the tibial nerve on a regular basis, it is also important to understand how well patients tolerate the device. In order to assess patient acceptance, a patient satisfaction grade will be documented for each subject at all follow-up visits.

32. Wagner, T. H., et al. "Quality of life of persons with urinary incontinence: development of a new measure." *Urology* 47.1 (1996): 67-71.
33. Hajebrahimi, Sakineh, et al. "Validity and reliability of the International Consultation on Incontinence Questionnaire-Urinary Incontinence Short Form and its correlation with urodynamic findings." *Urology journal* 9.4 (2012): 685.

3-7 Risk Analysis

3-7-1 Overview

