Serious: Results in death during the study period; is life-threatening; requires hospitalization or prolongation of existing hospitalization; results in persistent or significant disability or incapacity; results in a congenital anomaly or birth defect; requires medical or surgical intervention to preclude permanent impairment of a body function or to prevent permanent damage to a body structure, where the device is suspected to cause such intervention; other important medical events not captured by the other categories where the event may jeopardize the patient and may require medical or surgical intervention to prevent one of the other outcomes.

3-8-6-3-3 Expectedness

Expected: Any adverse reaction whose nature and intensity are consistent with that described under risk assessment.

Pivotal Study of Subcutaneous Tibial Nerve Stimulation with eCoin[®] for Urgency Urinary Incontinence.

Unexpected: Any adverse reaction not included under risk assessment.

3-8-6-4 Recording of Adverse Events

Expected device-related AEs will be recorded on case report forms as shown in Attachment 4-9, which are used at each visit. Unexpected or unrelated AEs or any requiring medical attention will be reported on CRFs and further recorded on AE forms. Subjects will be requested to report adverse urologic events that are inconsistent with their normal medical condition that occur in between visits to the study coordinator or medical staff who will record on AE forms. All adverse events will need to be evaluated and assigned by a medical reviewer on or designated by the Data and Safety Monitoring Board (DSMB) with regards to:

- 1) Relatedness or causality to the study device
- 2) Severity
- 3) Expectedness
- 4) Action taken

The Sponsor is responsible for determining if an adverse event is unexpected. If expectedness is assessed by a medical reviewer as unexpected, the Sponsor will be notified and will evaluate and assign a final determination that may or may not result in a requirement to report expeditiously to regulators, IRBs, or both.

At each contact with the subject, the Investigator will obtain information on AEs by specific questioning and examination. In the CRF for visits, if an event is reported, the AE checkbox will be selected. This selection will trigger a separate form to be filled out that records the following information:

1. Subject Number
2. Adverse Event (AE)
3. Date of AE onset
4. Date of AE cessation
5. Severity
6. Expectedness
7. Causality

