The primary effectiveness outcome is achieving at least a 50% reduction from baseline in the number of urgency urinary incontinence episodes per 24 hours on a 3 day voiding diary after 48 weeks of eCoin[™] tibial nerve stimulation.

The proportion of responders along with its 2-sided 95% exact Clopper-Pearson confidence interval will be summarized after 48 weeks of therapy.

3-9-3-3-2 Key Secondary Effectiveness Outcome

The key secondary effectiveness outcome is achieving at least a 50% reduction from baseline in the number of urgency urinary incontinence episodes per 24 hours on a 3 day voiding diary after 24 weeks of eCoin[™] tibial nerve stimulation.

Pivotal Study of Subcutaneous Tibial Nerve Stimulation with eCoin[®] for Urgency Urinary Incontinence.

The proportion of subjects with at least 50% reduction from baseline along with its 2-sided 95% exact Clopper-Pearson confidence interval will be summarized after 24 weeks of therapy.

3-9-3-3-3 Primary Safety Outcome

The primary safety outcome is device-related adverse events from implantation to 52 weeks after implantation of eCoin[™].

All device-related adverse events up to 52 weeks after implantation of eCoin[™] will be summarized by preferred term. Tabulations of these data will include the number of subjects exposed and the number of subjects with at least one device-related adverse event.

3-9-3-3-4 Key Secondary Safety Outcome

The key secondary safety outcome is device-related adverse events 28 weeks after implantation of eCoin[™].

All device-related adverse events up to 28 weeks after implantation of eCoin[™] will be summarized by preferred term. Tabulations of these data will include the number of subjects exposed and the number of subjects with at least one device-related adverse event.

3-9-3-3-5 Secondary Outcomes

The secondary outcomes listed in this section are based on data after 24 and 48 weeks from activation (28 and 52 weeks after implantation). These outcomes, which are for descriptive purposes, will not be formally analyzed statistically. The SAP will describe in detail analyses of the secondary outcomes.

- Achieving 75% improvement in the number of urgency urinary incontinence episodes per 24 hours on a 3 day voiding diary.
- Achieving 100% improvement in urgency urinary incontinence episodes (“Dryness”) per 24 hours on a 3 day voiding diary.
- Reduction from baseline in the number of urgency urinary incontinence episodes per 24 hours on a 3 day voiding diary.

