11.2. Assessment of the incision

All subjects will have an incision healing check visit two weeks after both implantation and explantation. Any adverse symptoms (site pain, site warmth, site swelling, fever, etc.) will be summarized by visit and severity (mild, moderate, or severe).

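### Protocol 3-8-6-4 directs subjects to report urologic events between visits, although the safety outcomes are device-related events of a leg implant, and its recording rules contradict each other

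*Protocol*

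**What the plan says.** **Outcome.** Protocol 3-9-3-3-3 reads: "The primary safety outcome is device-related adverse events from implantation to 52 weeks after implantation of" the device. The key secondary safety outcome (3-9-3-3-4) is the same at 28 weeks. Both are tabulated, with no performance goal or test.

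**Risks.** Section 3-7-4-3 lists bruising, incisional pain, paresthesia of the toes, foot or leg, wound complications, infection, stimulation discomfort, neuritis, extrusion, migration and similar events. Section 3-6 reasons from the premise "Given that the primary safety concern is infection" and expects the serious infections within the first month.

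**Reporting between visits (3-8-6-4).** "Subjects will be requested to report adverse urologic events that are inconsistent with their normal medical condition that occur in between visits". Staff then record these on AE forms.

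**Reporting at contacts (3-8-6-4).** "At each contact with the subject, the Investigator will obtain information on AEs by specific questioning and examination".

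**Recording (3-8-6-4).** Three sentences bear on the form to use:

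- The opening sentence covers what the sponsor anticipates from the device: "Expected device-related AEs will be recorded on case report forms as shown in Attachment 4-9, which are used at each visit".
- The second sentence adds a further form for another group of events: "Unexpected or unrelated AEs or any requiring medical attention will be reported on CRFs and further recorded on AE forms".
- A later paragraph makes no such division: "In the CRF for visits, if an event is reported, the AE checkbox will be selected. This selection will trigger a separate form". That form holds onset, cessation, severity, expectedness and causality.

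The section closes by identifying Attachment 4-9 as the sample AE report form.

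**Incision checks (SAP 11.2).** "Any adverse symptoms (site pain, site warmth, site swelling, fever, etc.) will be summarized by visit and severity". Nothing says whether these symptoms also enter the AE tables of SAP 11.1.

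**The concern.** The one request that the protocol makes of subjects between visits points at the bladder. The safety outcomes and the listed risks concern the implant site, the leg and the stimulation. A subject with two days of soreness over the device, or tingling after a session, has not been asked to call.

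The second problem is the form. Suppose a site follows the opening sentences of 3-8-6-4 and treats the visit CRF and the AE form as different documents. An expected device-related event that needs no medical attention then gets no separate form with an onset date and a causality rating. Another site, following the later sentence, completes one. The 28- and 52-week device-related tables need both items.

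This is a single-arm study meant to support a pre-market application, so no control group shares any under-ascertainment. Both problems would lower the device-related count.

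**Working it through.** The plan states no figure for AE capture, so there is nothing to reproduce. The check compares the sections and then computes the visit gaps.

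**1. Does anything else ask for implant-site events between visits?** Not in the text available. The reminder calls in 3-4-2 concern the diary. Section 3-4-8 covers wound-care instruction. SAP 11.1 says that AEs are monitored continuously but gives no mechanism. The consent form, brochure and manuals are attachments whose content is not in the file, so they cannot be checked.

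**2. How long are the intervals?** Inputs are the windows in Protocol 3-4-2, in days from activation: week 12, 79–89; week 24, 163–173; week 36, 247–257; week 48, 331–341.

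Nominal gap = difference of window midpoints; shortest = earliest next day minus latest previous day; longest = latest next day minus earliest previous day.

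| Gap | Nominal | Shortest | Longest |
|---|---|---|---|
| Week 12 to 24 | 168 − 84 = 84 | 163 − 89 = 74 | 173 − 79 = 94 |
| Week 24 to 36 | 252 − 168 = 84 | 247 − 173 = 74 | 257 − 163 = 94 |
| Week 36 to 48 | 336 − 252 = 84 | 331 − 257 = 74 | 341 − 247 = 94 |

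Earlier gaps are 28 days nominal. A reprogramming visit held on a separate day (9b or 10b) can shorten a later gap, at the least to 247 − 180 = 67 days, but does not remove it.

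The three long gaps total 3 × 12 = 36 weeks. That is 36/52 = 69% of the primary safety window, or 36/48 = 75% of the time after activation. The 28-week window contains one of them: 12/28 = 43%.

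**3. Which events are exposed?** The severity scale in 3-8-6-3-2 describes mild events as transient or lasting under 48 hours. Such an event early in a long gap is over about 80 days before the next scheduled questioning. Stimulation runs automatically, every 4 days after week 18 (3-8-2), so each of the last two gaps holds about 84/4 = 21 sessions away from the clinic. Remote visits under the COVID-19 provisions in 3-4 are reviewed by telephone, which limits examination of the leg.

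**4. What do the recording rules give?** Take an expected device-related AE that needs no medical attention and is reported at a visit.

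| Rule followed | Separate AE form? |
|---|---|
| Opening two sentences, visit CRF distinct from AE form | No |
| Opening sentence, Attachment 4-9 read as the AE form | Yes, but the second sentence then draws an empty distinction |
| Later checkbox sentence | Yes, with no exception for expected events |

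The rules cannot all hold, and the attachment reference is part of the conflict.

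**The case against.** The case for leaving the plan alone has force. Subjects are not told to withhold other events. The AE definition in 3-8-6-2 covers any untoward occurrence and names the implant site among related events. AEs are sought at every contact, and all go to a medical reviewer. The week 2 healing check and week 4 activation visit, both with photographs and AE assessment, fall where the protocol expects serious infections. The safety outcome is descriptive. All of this stands, and it narrows the exposure to mild or self-limiting events in the long gaps.

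Four stronger readings are tempting, and the documents do not support them:

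- *Expected device-related events have a settled lighter route and drop out of the primary count.* The checkbox sentence contradicts this. Attachment 4-9 is itself the AE form, Protocol 3-9-1 lists the AE form among the CRFs, and SAP 11.1 does not restrict its tables to events on a separate form. The defect is a contradiction.
- *The loss can be sized from the hypertension study*, where 9 of 48 subjects had incision-site or hand inflammation, tenderness or redness (2-2-2-3): 9/48 × 120 = 22.5 subjects. That assumes every such event goes unrecorded, and no miss rate is given. It also borrows from a study with 96 median-nerve implants in 48 subjects. The four infections in that study were treated, so comparable events here would reach AE forms as medically attended.
- *The 48-week gaps in the extension make it worse.* They lie outside the 28- and 52-week windows.
- *Device events are the ones collected least completely.* Questioning at every contact and the early checks say otherwise.

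On SAP 11.2, a separate symptom table does not exclude those symptoms from 11.1, since AE assessment is scheduled at the same visits. What remains is that the SAP does not state the link.

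**Conclusion.** The point holds in limited form and should be corrected. The between-visit request does not match the safety outcomes or the listed risks, and 3-8-6-4 contradicts itself on recording.

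The exposure is mainly mild or transient device-related events in three gaps of 84 days nominal (74 to 94 between main visits), which make up 69% of the 52-week window. This percentage is exposed time, not lost events. How many would be missed cannot be derived from the documents; only the direction can be given, towards a lower device-related count. The conclusion assumes that the attachments not in the file contain no broader instruction. If the subject materials already ask for implant-site symptoms, the first part reduces to aligning the protocol with them, and the recording conflict remains. No sample-size, power or effectiveness figure is affected.

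**What to change.** 1. In Protocol 3-8-6-4, broaden the between-visit request to: *any adverse event, including any symptom at the implant site, in the implanted leg or foot, or with stimulation*. Carry the same wording into the subject materials.
2. State one recording rule: every AE, expected or not, goes on the AE form with onset date and relatedness. Remove the sentences that split recording by expectedness.
3. Correct the Attachment 4-9 reference so that it denotes the AE form throughout.
4. In SAP 11.2, state that incision-check symptoms meeting the AE definition are also entered as AEs and counted in SAP 11.1.

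The cost is a wording amendment, more AE forms for minor events, and probably a somewhat higher reported device-related rate.
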